3.3 INFECTIOUS, OCCUPATIONAL AND ENVIRONMENTAL FACTORS

An interviewer-administered occupational / environmental questionnaire is used to obtain information to address the following hypotheses:

- Sarcoidosis patients (cases) are more likely to report employment in particular occupations or occupational categories when compared with a non-sarcoidosis referent group (controls). The categories considered include:
 - A. Employment in metal dust and metal fume associated industries.
 - B. Employment as health care workers.
 - C. Employment as child care providers and educators.
 - D. Employment as firefighters.
 - E. Employment in the military.
 - F. Employment in agriculture.
 - G. Occupational exposure to organic dusts.
 - H. Employment in mechanically ventilated buildings.
 - I. Employment in environments where exposure to microbial bioaerosols occurs.
 - J. Occupational exposure to chemicals that can produce hypersensitivity pneumonitis or granulomatous lung disease (e.g., isocyanates, pyrethrums).
 - K. Employment indoors.
 - L. Employment in dusty trades.

- M. Frequent close contact with co-workers or others during the work day.
- 2. Sarcoidosis patients (cases) are more likely to report particular environmental exposures when compared with a non-sarcoidosis referent group (controls). The exposures considered include:
 - A. Avocational exposure to metal dust and fumes (e.g., welding, jewelry making).
 - B. Avocational exposure to children.
 - C. Exposure to microbial contamination and bioaerosols in the home environment.
 - D. Exposure to organic dusts in a home environment.
 - E. Tobacco exposure.
 - F. Prior use of medications known to produce hypersensitivity lung diseases or granulomatous disease in other organs.
 - G. Rural residence.
 - H. Exposure to animal (including bird) antigens.

As part of the occupational and environmental questionnaire, antecedent occupational histories are recorded. Case and control occupations and industries are coded using standardized industrial codes (SIC) and standardized occupational codes (SOC) to test the following hypotheses:

 Sarcoidosis patients (cases) are more likely to have been employed in certain occupational categories or industries when compared with a non-sarcoidosis referent group (controls).

Specifically, we propose to test the hypothesis that occupational categories sharing common chemical or biological material exposures confer similar risks of sarcoidosis.

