3.4 SOCIOECONOMIC FACTORS

We are studying how race, socioeconomic status (SES), and medical care use and access are associated with sarcoidosis disease status at presentation and disease progression over time. Specifically, we will test the hypotheses that: sarcoidosis patients will be more likely to be of low SES than controls; sarcoidosis patients with low SES will present with more severe disease and have greater disease progression in two years than patients with high SES; sarcoidosis patients with low SES will have less access to medical services than sarcoidosis patients with high SES; and sarcoidosis patients with low SES will comply less with medical treatment (including adherence to medication), return less regularly for follow-up visits and maintain less continuity of care than patients with high SES. Similar relationships are expected in all racial groups.

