12.2.3 Subgroup Analyses

As part of ACCESS, Clinical Center investigators may want to make comparisons of cases and controls within certain strata. For instance, there could be comparisons of female cases and controls, comparisons of black cases and controls, and comparisons of erythema nodosum cases with their matched controls. Each of these subgroup comparisons will bring with it a different number of cases and controls and power for making comparisons. Effect sizes that could be detected in one subgroup analysis, might not be detected in another analysis. Power analyses have been performed for statistical comparisons that will be performed in subgroups representing 7%, 14%, 25%, 50% and 75% of the entire case control study population. These percentages may be representative of comparisons for a small substudy (7% and 14%), within a sarcoidosis category (20%), within a gender comparison (50%), and within the black population (75%, published reports put the percentage of sarcoidosis cases who are black between 60% and 80% in some cities). Power calculations for binary exposure variables when performing analyses in subgroups are presented in Tables 3 through 12. There is a substantial change in the odds ratios that can be detected with adequate power depending upon the number of cases in the subgroup. For instance, fixing the odds ratio at 0.7, the correlation between case-control response at 0.5, and the proportion of controls exposed at 0.3, there is 54.8%, 83.7% and 95.0% power to detect this odds ratio for 180, 360 and 540 case control pairs, respectively.

As part of each subgroup analysis, a statistical test will be performed to determine if the findings relating to exposures in one subgroup correspond to the findings in the complimentary subgroup (an interaction test). For instance if a risk factor is discovered for females, is that risk

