factor also present and at the same level of magnitude in males or is it different. For binary exposure variables a matched case control regression model will be used with terms for the subgroup, the exposure, and the exposure-subgroup interaction in the model. For a case control design with one case and one control, the Cox Proportional Hazards model can be used by creating a dummy variable that always lists the case and "failing" first with control "censored" after the case "failure time". Power calculations for the factorial term in the Cox Model have been published (Peterson and George, 1993). In general the statistical efficiency of the interaction test is lower than the main effects test. For instance, with 50% of the population in one subgroup and 50% in the complimentary subgroup, the efficiency of the interaction test is one half that of the main effects test.

As an example, the current study design has at least 80% percent power to detect an odds ratio of 1.25 when the exposure variable of interest has a 30% prevalence and the test is being performed at the 5% alpha level. Now let us consider a statistical interaction test of an exposure between two groups. The test would be designed to determine if the ratio of the two odds ratios in the two groups were different or the same. Specifically, the interaction test is a test of whether the ratio of these two odds ratios is one. To be able to detect a ratio of the two odds ratios that is 1.25 or larger with 80% power with an exposure variable with a 30% prevalence and testing at the 5% alpha level would require twice the number of case control pairs or 1,440 cases. With 720 cases, there is at least 80% power to detect a ratio of two odds ratios on the order of magnitude of 1.38. This is not substantially different from the operating characteristics of the main effect comparisons. Thus there will be adequate power to detect small interactions with the proposed sample size.

For continuous variables, there is little impact on the power of proposed analyses to detect meaningful differences between case and control means in each of the above subgroup sizes. With 180 cases in a subgroup, it will be possible to detect differences of 0.34 standard deviations with 90% power when testing at alpha 0.05 (two sided test).

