Statistical analyses for probability inference based on these estimates can also be performed using conditional logistic regression (Breslow et al, 1978). This model is robust in the sense that it will allow for the inclusion of effect modifiers or risk factors. Effect modifiers are variables that change the exposure-risk odd ratios for the disease. It will not be possible to estimate odds ratios for age, gender, or race since these are matching variables. However, it will be possible to include interaction terms between gender, race, or age and other exposure variables to determine if the odds ratio estimates for these other variables are homogenous in males and females or blacks and whites. In some situations, analyses will be required to determine if one type of exposure (e.g., occupational) is associated with a genetic predisposition of sarcoidosis. These analyses will be done using the conditional logistic regression model in a matched case control format. Tests of the effect modification of the exposure will be done using an interaction variable in the conditional logistic model. Conditional logistic regression will be performed using the PHREG procedure in SAS.

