12.3.4 Analyses for the Clinical Course Study

A key feature of the clinical course study is the different length of time that cases will be followed. Cases will be recruited over a one-year time period, and will be followed for a maximum of two years.

It is planned to analyze follow-up data using: the Generalized Estimating Equations (Liang and Zeger, 1986; Zeger and Liang, 1986) program that runs under the SAS system using IML or the longitudinal data analysis methods of Laird and Ware (Laird and Ware, 1982), using Proc MIXED, a SAS procedure. Both of these models are robust in that they will allow for the inclusion of correlations and dependence structures in the serial data being collected for each of the cases. The models have the added advantage that the results are presented much like the results from more standard linear models. These models can be used to analyze outcome measures with continuous distributions, and outcomes that are binary or categorical. Both models will allow for the inclusion of fixed covariates or time-dependent covariates (variables that change over the course of time, and influence the risk of progression or regression of disease in accordance with these variations).

The dependent variables that can be structured in the form of a time-to-event, survival analysis techniques will be most appropriate for this type of analysis. Event rates could be calculated using Kaplan-Meier estimates (Kaplan and Meier, 1958), and confidence intervals can be obtained using Greenwood's formula (Greenwood, 1926). If multivariate analyses are contemplated, the Cox proportional hazards model (Cox, 1972) could be used to perform multivariate analyses. This model will also accommodate the inclusion of fixed and time-dependent covariates, and allows for differences in the length of time that cases will be in follow-up. Tests for

interactions can be included in all of the above models. Dependent variables of interest will include measures of progression and regression of sarcoidosis symptoms.

12.3.5 "Synthetic Case Control" Studies

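### Section 3.3 proposes to test that job categories carry similar risks, but Chapter 12 offers only a test of difference, described as able to show sameness

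*Protocol*

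**What the plan says.** Protocol section 3.3, on coded occupations and industries, states: "we propose to test the hypothesis that occupational categories sharing common chemical or biological material exposures confer similar risks of sarcoidosis". It gives no limit for how close the risks must be to count as similar.

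Chapter 12 supplies one tool for comparing odds ratios. Section 12.2.3 begins: "As part of each subgroup analysis, a statistical test will be performed to determine if the findings relating to exposures in one subgroup correspond". Its worked example gives the purpose, "The test would be designed to determine if the ratio of the two odds ratios in the two groups were different or the same", and then the null hypothesis: "the interaction test is a test of whether the ratio of these two odds ratios is one". Section 12.3.2.2 puts interaction terms into the conditional logistic model "to determine if the odds ratio estimates for these other variables are homogenous in males and females or blacks and whites". For the clinical course study, section 12.3.4 says only that tests for "interactions can be included in all of the above models".

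Section 3.4 lists directional socioeconomic hypotheses and then adds: "Similar relationships are expected in all racial groups". Section 12.3.2.2 plans 95% confidence intervals for matched-pair odds ratios and for mean differences. It names none for a ratio of two odds ratios.

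**The concern.** In a test of ratio = 1, similarity is the null hypothesis. Rejection supports a difference. Non-rejection supports nothing unless the confidence interval is also shown to be narrow. Section 12.2.3 gives the test two possible verdicts when it can deliver only one.

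This matters most for the occupational hypothesis, because there similarity is the claim under test. Some of the job categories in section 3.3, such as firefighters, may well be rare, and section 1.5.1 stresses low-prevalence exposures. If two rare jobs are compared and the test is non-significant, the wording makes it natural to report that they carry the same risk, and hence that their common exposure is a plausible agent, when the data may be compatible with anything from no difference to a several-fold one.

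**Working it through.** **The plan's own figure.** Section 12.2.3 states 80% power for a ratio of odds ratios of about 1.38 with 720 pairs at 30% prevalence. The section 12.2.1 formula is power = Φ(δ√(N/ψ) − 1.96), with ψ = p1 + p0 − 2p1p0 − 2cov.
- For odds ratio 0.7, p0 = 0.3 and correlation 0.5 it gives 54.8%, 83.7% and 95.0% for 180, 360 and 540 pairs, as the protocol prints.
- For odds ratio 1.25 with 720 pairs it gives 79.6% at correlation 0.5 and 50.7% at correlation 0.
- Taking the protocol's one-half efficiency, exp(√2 × ln 1.25) = 1.37, so 1.38 is reproduced at correlation 0.5.

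On that figure the standard error of the log ratio is ln 1.38 / (1.96 + 0.84) = 0.115. A true ratio of 1.25 then gives ln 1.25 / 0.115 = 1.94, and the chance of non-significance is Φ(1.96 − 1.94) = 51%. Even on the plan's own terms, a non-significant result is weak evidence of similarity.

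**The occupational comparison.** Inputs from the protocol are 720 pairs, two-sided 0.05, and control frequencies p of 1%, 2.5%, 5% and 10% (columns of Tables 1 to 12). My assumptions are two mutually exclusive jobs A and B, each held by a proportion p of controls; true odds ratios 2.0 and 1.0; independence within pairs; and a Wald test of equal log odds ratios in the conditional logistic model.

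Case frequencies are 2p/(1+p) for A, p/(1+p) for B and (1−2p)/(1+p) for neither. Each type of discordant pair, with expected counts a and b in its two directions, contributes information w = ab/(a+b). Then

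Var(log ratio) = 1 / [w_AB + w_A0·w_B0 / (w_A0 + w_B0)].

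At p = 5%:
- A versus neither: counts 61.7 and 30.9, w = 20.57
- B versus neither: counts 30.9 and 30.9, w = 15.43
- A versus B: counts 3.43 and 1.71, w = 1.14

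The bracket is 1.14 + 20.57 × 15.43/36.00 = 9.96, so SE = 0.317. The standardised difference is 0.693/0.317 = 2.19, and the miss rate is Φ(1.96 − 2.19) = 41%.

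| Controls in each job | SE | ln 2 / SE | Difference missed |
|---|---|---|---|
| 1% | 0.700 | 0.99 | 83% |
| 2.5% | 0.445 | 1.56 | 66% |
| 5% | 0.317 | 2.19 | 41% |
| 10% | 0.228 | 3.05 | 14% |

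Simulation of 1,500 studies per cell gives 84%, 66%, 41% and 14%. For odds ratios 1.5 and 1.0 the same formula gives about 91%, 85%, 76% and 57%.

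**Sensitivity to the correlation.** Section 12.2.1 uses correlations 0.5 and 0.0; the table uses 0.0 only. For a two-subgroup comparison at 30% prevalence and a true ratio of 1.5, the miss rate on the protocol's marginal odds-ratio scale is 28% (correlation 0.5) to 56% (correlation 0) for a 50/50 split, and 41% to 65% for 75/25. On the conditional matched-pair scale, correlation 0.5 makes matters worse: about 76% and 81% with a common odds ratio of 1. The size depends on correlation and scale; the logic does not.

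**What a margin rule would deliver.** If both jobs have odds ratio 1, the variance reduces to 4/(720p), so SE = 0.471, 0.333 and 0.236 at 2.5%, 5% and 10%. With an example margin of 0.5 to 2.0 and a 90% interval, the chance of a correct claim is 2Φ(0.693/SE − 1.645) − 1, taken as 0 when negative: 0%, 34% and 80%. If both odds ratios are 2.0 (SE = 0.413, 0.296, 0.213) it is about 3%, 52% and 89%.

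**The case against.** The case against has several parts, and some of it stands.

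- A reader might infer two tested similarity hypotheses. The sentence in section 3.4 is an expectation placed after the list of hypotheses to be tested. It is a secondary example only.
- A reader might infer that the plan will report p > 0.05 as proof of similarity. No section says so. The wording invites that reading but does not require it.
- No section assigns the interaction test to comparing job categories; sections 12.2.3 and 12.3.2.2 describe it mainly for strata of people. The two-job Wald test above is therefore a stand-in. The section 3.3 sentence could also be read as a rationale for grouping occupation codes by shared exposure. Yet it says that the hypothesis will be tested, and Chapter 12 offers no other comparison of odds ratios.
- A reader might infer that a missed doubling is the likely outcome at the protocol's exposure frequencies generally. That holds at 1% and 2.5%, but at 5% and 10% detection is more likely.
- Margins are often left to a statistical analysis plan, which is not shown, and section 3.7 describes ACCESS as generating hypotheses. So the missing margin is not itself the error. The error is in what the protocol does fix: a similarity hypothesis, and a stated purpose that the test cannot serve. A hypothesis-generating aim favours estimation over a same-or-different verdict.
- The planned 95% intervals help, but none is stated for the ratio of odds ratios, which is the quantity in question.

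**Conclusion.** The point holds for one stated hypothesis, the occupational one in section 3.3, and for the description of the interaction test in sections 12.2.3 and 12.3.2.2. A test of ratio = 1 cannot establish that risks are the same, whatever its power.

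The miss rates of about 83%, 66%, 41% and 14% show why the distinction matters in practice. They rest on 720 pairs, independence within pairs, two exclusive jobs of equal frequency and true odds ratios of 2.0 and 1.0. They illustrate how little non-significance would mean for rare jobs; they do not predict how the investigators will report.

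**What to change.** In sections 3.3, 12.2.3 and 12.3.2.2:

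1. Restate the aim as estimating how far risks differ between job categories that share an exposure, and report the ratio of odds ratios with its confidence interval.
2. In section 12.2.3, delete the closing words that offer sameness as a verdict of the interaction test.
3. State that a non-significant interaction test is not evidence of similarity. Apply the same statement to the homogeneity wording in section 12.3.2.2 and to any comment on the expectation in section 3.4.
4. Allow the word 'similar' only if the interval lies inside a margin that the sponsor fixes before analysis; otherwise report 'inconclusive'. The 0.5 to 2.0 margin used above is an example. The sponsor may want a tighter one, since section 1.5.1 sizes the study for odds ratios of two.

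No new data are needed. The cost is fewer similarity claims: at a two-fold margin, almost none for jobs held by about 2.5% of controls or fewer, roughly a third to a half of truly equal pairs of jobs at 5%, and most at 10%.

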3.4 SOCIOECONOMIC FACTORS

We are studying how race, socioeconomic status (SES), and medical care use and access are associated with sarcoidosis disease status at presentation and disease progression over time. Specifically, we will test the hypotheses that: sarcoidosis patients will be more likely to be of low SES than controls; sarcoidosis patients with low SES will present with more severe disease and have greater disease progression in two years than patients with high SES; sarcoidosis patients with low SES will have less access to medical services than sarcoidosis patients with high SES; and sarcoidosis patients with low SES will comply less with medical treatment (including adherence to medication), return less regularly for follow-up visits and maintain less continuity of care than patients with high SES. Similar relationships are expected in all racial groups.

3.5 PSYCHOSOCIAL FACTORS AND QUALITY OF LIFE

The impact of sarcoidosis can be measured not only in physical changes, but behavioral, emotional and cognitive outcomes as well. The measurement of these domains reflects an awareness that diseases and their treatment may influence these "quality of life" variables. The physical consequences of sarcoidosis (pain, shortness of breath, changes in appearance, lethargy) and its associated treatment regimens may diminish quality of life by negatively influencing functional status, mood, self-esteem, and interpersonal relations. The impact of sarcoidosis and its associated treatment on a patient's functional capacity and quality of life has received virtually

3-4

no scientific study. Patients report psychosocial dimensions of the disease, such as depression, anxiety, isolation, powerlessness, low self-esteem, poor body image and social issues as key concerns in disease management. Psychosocial and behavioral variables have been shown to be important pre-disposing factors in the etiology of other diseases (e.g., cardiovascular, cancer, diabetes) and to be mediators of disease morbidity and mortality. Given the absence of psychosocial data related to the etiology and course of sarcoidosis, it is timely and cost-effective to incorporate such assessment into this unique study. This project will provide valuable new data in this area. We hypothesize that:

- 1. Cases with symptomatic disease at baseline will report significantly poorer health-related quality of life and greater depression than healthy community controls.
- Higher baseline levels of optimism and social support, and lower levels of depression will be associated with higher baseline levels of health-related quality of life in both cases and controls.
- 3. Baseline levels of depression, social support, and optimism will predict poorer medication adherence and follow-up outcomes, independent of baseline disease severity. Data to test these hypotheses are collected using the Medical Outcomes Study 36-item Short-Form Health Survey (SF-36), the Center of Epidemiologic Studies Department (CES-D) scale, the Medical Outcomes Study Social Support Scale (MOS-SSS), the Life Orientation Test (LOT) and two study-specific questions concerning medication adherence.

3.6 SPECIAL LABORATORY STUDIES

In June 1996 the ACCESS Principal Investigators set priorities among proposed special laboratory studies to incorporate the highest priority studies in the ACCESS Protocol. Five studies were selected as consistent with the scientific approach in ACCESS and available resources. Progress in each project will be reviewed by the Principal Investigators and DSMB 18 months after the start of support for the special laboratory studies. Progress is assessed based on complete reports on methods development, case and control enrollment, specimen accession, and

preliminary data. Funding for two additional studies was provided by NHLBI in May 1997; progress for these studies will also be reviewed 18 months after the start of funding. Brief descriptions of these studies follow; more detailed descriptions of study methods are found in the ACCESS Procedures Manual Volume IV.

3.6.1 HLA Typing in Sarcoidosis

ACCESS will investigate HLA Class II associations with sarcoidosis and correlate any associations with the environmental history to identify possible causative agents. PCR with sequence specific oligonucleotide (SSO) probes will be used to determine the molecular sequence of HLA Class II DR, DQ and DP beta genes from cases with newly diagnosed sarcoidosis and controls. Any genes that can not be identified using SSO probes will be cloned and sequenced. The specific aims are:

- A. Determine which alleles are associated with sarcoidosis and which alleles are protective.
- B. Determine which amino acids in the pockets that bind antigenic peptides are associated with sarcoidosis and which are protective.
- C. Determine interactions between alleles or amino acids in the binding pockets that are associated with sarcoidosis and specific environmental exposures such as exposure to metals and infectious agents.
- D. Determine whether alleles or amino acids in the binding pockets that are associated with sarcoidosis are also associated with specific clinical syndromes (e.g., erythema nodosum, extrapulmonary sarcoidosis, persistent sarcoidosis) among cases.

The case control design is the ideal method to investigate relationships between genetic and environmental factors in disease. Class II molecules are known to be involved in sarcoidosis -- both from the presumed pathophysiology and genetic studies. If specific alleles or amino acids in the binding pockets are found to be associated with sarcoidosis, informative next steps would be immunoprecipitation of Class II molecules with bound antigenic peptide and identification of the
possible etiologic agents that contain those peptides because they may be the etiologic agents of sarcoidosis.

